3. OBJECTIVES OF THE STUDY

MAIN GOAL

- To evaluate the effectiveness of the application of Theraband® techniques on the strength of the external rotator muscles of the rotator cuff of the shoulder in amateur swimmers between 18 and 33 years of age.

SECONDARY OBJECTIVES

- To evaluate the effectiveness of the application of Theraband® techniques on the range of motion of the shoulder in amateur swimmers between 18 and 33 years of age.
- To evaluate the effectiveness of the application of Theraband® techniques on the scapular displacement of the shoulder in amateur swimmers between 18 and 33 years of age.
- To evaluate the effectiveness of the application of Theraband® techniques on the muscular balance of the rotator cuff of the shoulder in amateur swimmers between 18 and 33 years of age.

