- Joint range of motion in external rotation. The patient will be placed in the supine position on a table with the arm stabilized and a towel placed below the humerus to maintain a position of the arm 10/15° anterior to the coronal plane (in the scapular plane). The patient's arm will be in a 90° shoulder abduction position, the elbow outside the table at 90° flexion, the forearm and wrist in a 0° position (perpendicular to the table and the floor). To carry out the measurement, a goniometer (Tandou_1AA800252®) will be used. The axis will be placed over the central part of the acromion. The fixed arm of the goniometer will be positioned aligned with the vertical perpendicular to the ground, while its mobile arm will be superimposed on the fixed arm, aligned with the longitudinal midline between the ulna and its styloid process (14).
- Rotator cuff muscle balance: with the results of the maximum isometric strength assessment, we will make a ratio between internal and external rotators of each arm (maximum internal rotation isometric force / maximum external rotation isometric force), a value closer to 1 will indicate a better muscular balance (15).
- Scapular displacement: in standing position, the horizontal distance between the inferior angle of the scapula and the corresponding thoracic spinosa is measured in the relaxed position as a baseline measure, and the horizontal displacement of the angle at maximum elevation of the arm is measured using the PALM(16).
- inter-observer reliability analysis will be performed. The principal investigator and the evaluator will evaluate the maximum isometric force of the external rotators of the shoulder and the angle of optimal application of force in a sample of 5 subjects.

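### In section 4.6 the goniometer axis (acromion) and the mobile-arm landmark (ulna) cannot both be met in the stated position, so the assessor has to improvise the external-rotation reading

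*Combined protocol and SAP*

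**What the plan says.** Section 3 lists range of motion first among the secondary objectives: "To evaluate the effectiveness of the application of Theraband® techniques on the range of motion of the shoulder in amateur swimmers". Section 4.6 defines the measure as "Joint range of motion in external rotation", taken with a goniometer and referenced to item 14 of the bibliography.

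The instructions in section 4.6 are these:

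- **Position.** Supine, with a towel under the humerus. "The patient's arm will be in a 90° shoulder abduction position, the elbow outside the table at 90° flexion". The forearm starts vertical, and this is called 0°.
- **Axis.** "The axis will be placed over the central part of the acromion".
- **Fixed arm.** "The fixed arm of the goniometer will be positioned aligned with the vertical perpendicular to the ground".
- **Mobile arm.** Laid over the fixed arm and "aligned with the longitudinal midline between the ulna and its styloid process".

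The section does not say how the mobile arm is placed at end range. Nothing elsewhere in the document changes the axis landmark.

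**The concern.** With the shoulder abducted and the elbow bent to a right angle, rotating the shoulder swings the forearm about the long axis of the humerus. The ulna meets that axis at the elbow. The plan centres the instrument at the other end of the humerus and still asks for its arm to follow the ulna. The arms of a goniometer radiate from its axis, so one of the two instructions has to give way, and the plan does not say which.

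What is at stake is the precision and scale of the range-of-motion outcome. If the assessor resolves the conflict differently from one subject or visit to another, the difference enters the pre-to-post change as error. In a trial of 30 subjects such noise is costly. The planned inter-observer check would not reveal it: it covers external rotator force and the angle of optimal force application in 5 subjects, and leaves out range of motion.

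**Working it through.** The plan gives no figure to reproduce, so the check is geometric.

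**Inputs from section 4.6.** Abduction 90°, elbow flexion 90°, forearm vertical at 0°, axis on the acromion, fixed arm vertical, mobile arm along the ulna.

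**Assumed inputs, not in the documents.** Acromion to elbow *h* = 25-33 cm; elbow to ulnar styloid *f* = 25-27 cm. The humerus is taken as horizontal, and the 10-15° offset produced by the towel is ignored.

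**Step 1: can both landmarks be met?** Put the acromion at the origin, the elbow at (*h*, 0, 0) and the vertical along the third coordinate. At rotation *t* the ulna points along (0, sin *t*, cos *t*). The line from acromion to elbow is perpendicular to that direction for every *t*, so the nearest point of the ulna's line to the acromion is the elbow, at distance *h*. The gap is one full upper-arm length at every angle. It depends only on the elbow being at 90°, not on the assumed lengths or on ignoring the towel. Both landmarks cannot be met.

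**Step 2: what does each improvised placement read?**

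- *Axis at the elbow, arm on the ulna.* The angle to the vertical is *t*.
- *Axis at the acromion, arm held parallel to the ulna.* The angle is arccos(cos *t*) = *t*. True 0, 30, 60, 90 and 110° read 0, 30, 60, 90 and 110°.
- *Axis at the acromion, arm aimed at the styloid.* The angle is arccos(*k* cos *t*), where *k* = *f* / √(*h*² + *f*²).

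**Step 3: size of the distortion in the third case.** *k* falls as *h*/*f* rises, so the extremes lie at 33/25 and 25/27.

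| *h* / *f* (cm) | *k* | True 0° reads | True 90° reads | True 100° reads | A true 10° gain from 90° reads |
|---|---|---|---|---|---|
| 25 / 27 | 27/√(625+729) = 0.734 | 43° | 90° | 97.3° | 7.3° |
| 30 / 25 | 25/√(900+625) = 0.640 | 50° | 90° | 96.4° | 6.4° |
| 33 / 25 | 25/√(1089+625) = 0.604 | 53° | 90° | 96.0° | 6.0° |

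A true 10° gain would therefore be understated by 27% (10 − 7.3 = 2.7) to 40% (10 − 6.0 = 4.0).

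**Step 4: is the third case compatible with the text?** Not at the start position. An arm aimed from the acromion at the styloid stands 43-53° from the vertical when true rotation is 0°, whereas the plan has the two arms superimposed there.

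**The case against.** The strongest reply is that a goniometer reads the angle between the directions of its arms, wherever its centre sits. Section 4.6 fixes both directions: one vertical, the other along the ulna, coinciding at a 0° start. The angle between them is external rotation. This stands. A reader might infer from the misplaced axis that the outcome as written is not the external-rotation angle at all. The documents do not support that: two of the three workable placements read it exactly, and the third contradicts the superimposed start.

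The reply does not make the instruction workable. Holding an arm parallel to a bone one upper-arm length away is itself an improvisation that the plan does not describe. The superimposed position is given only for the start, and the end-range placement, which supplies the result, is left open.

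A second reply is that sections 4.5 and 4.6 have a blinded assessor, and section 4.6 has the same investigator repeat the assessment by the same guidelines. A reader might infer a false group difference from the landmark conflict. Nothing supports that, since a consistent placement affects both groups alike. Even the compressed scale is nearly linear around 90°, and a purely linear rescaling leaves the F statistic and partial eta squared of the planned mixed ANOVA unchanged. Repeating the same guidelines does not settle placement, however, when those guidelines cannot be followed, and blinding does not remove random placement error.

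Third, the cited source was not available, so whether it contains the same landmark is unknown. The finding rests only on the positions that the plan itself states.

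**Conclusion.** The axis instruction is wrong as written, and the severity is minor. The incompatibility of the two landmarks is certain for an elbow at 90°. The consequence is an ambiguous procedure and a risk of avoidable measurement error in a secondary outcome; the main objective, external rotator strength, is untouched.

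The 6.0-7.3° reading of a true 10° gain bounds the least favourable placement under the assumed lengths. It is not an estimate of what will happen in the trial. It applies only if the assessor aims from the acromion, against the stated start condition.

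**What to change.** Before the first baseline measurement, replace the axis sentence in section 4.6 with one to this effect: the axis is placed over the olecranon, in line with the long axis of the humerus; the fixed arm is vertical; the mobile arm lies along the ulna to its styloid process, at the start and at end range. Leave the rest of the positioning as it is, and use this placement at both the pre- and post-treatment assessments. With the axis there the instrument reads rotation directly: 0° at the start and 90° at 90°.

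The cost is one sentence in the protocol and a short briefing of the assessor, with no added equipment, visits or subjects. It has to be done before baseline, because readings taken with an unrecorded placement cannot be corrected afterwards.

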4.7. INTERVENTION

Each session will last approximately 4 minutes per subject, taking place 2 days a week, over a period of 8 weeks. The intervention will be carried out at the beginning of the training session.

Prior to the realization After swimming training, the strength technique with Theraband[®] will be applied to the subjects of the experimental group, asking the control group to follow their usual routine.

The Theraband® intervention will consist of the application of the protocol described by Batahla et al. 2015(1). The objective of the application of the technique is to produce an increase in muscle strength in the external rotators and the optimal angle of force application. The technique will be performed with the patient in a standing position lateral to a wall bar where the elastic band will be fixed at the level of the iliac crest. Each repetition will consist of bringing the end of the elastic band following the diagonal pattern of Kabat D2 for the flexion. It will start from a position of adduction, extension and internal rotation of the shoulder with elbow extension and pronation, flexion and ulnar tilt of the wrist until reaching a position of flexion, abduction and external rotation of the shoulder with elbow extension and supination, extension and radial bend of the wrist. The elastic bands used will have different resistances depending on the color. 2 types of bands will be used respectively from lower to higher resistance. There will be 3 series, of 10 repetitions each, for each upper limb. At the end of each series, the subjective perception of effort of each patient will be evaluated (from 0 to 10), and in the event that it reaches a value equal to or less than 6, 5 repetitions will be added in each series until reaching a maximum. of 20 or SPE greater than 6. When 20 repetitions are reached, the resistance of the Theraband® will be increased by changing the elastic band in the next session, starting again with 10 repetitions (1).

Subjects will be properly instructed in performing the exercises at the start of the protocol by physiotherapists and/or qualified trainers previously trained by the authors.

